1. VERSION HISTORY

This Statistical Analysis Plan (SAP) for study A4091056 is based on the Protocol Amendment 1 dated 23Sep2015.

Table 1. Summary of Major Changes in SAP Amendments

SAP Version	Change	Rationale
1.0	Not Applicable	Not Applicable
2.0	Throughout	The changes described below reflect updates from blinded data reviews and program decisions for alignment of analysis. Additionally, clarifications, removal of redundant text, and correction of typos have been implemented.
	Section 2.2, 3.5.1, 3.5.2, 6.6.1	clarified that various safety results will be presented by treatment period, safety follow-up period, and overall
	Section 3.2.1	removed Week 24 (off-treatment period) from some categorical endpoints
	Section 3.4, 5.3	clarified baseline diary pain scores are from the 3 most recent days of the 7-day pre-dose period
	Section 3.4.1, 5.2.2	added listing of mis-matches in stratification variables; removed some interaction analyses and sensitivity analysis with no covariates
	Section 3.5.2	clarified summaries of consultations
	Section 3.5.3	simplified total joint replacement and joint event summary descriptions
	Section 3.5.4	removed Survey of Autonomic Symptoms analysis by gender
	Section 4.2	added description of Per Protocol (PP) population process
	Section 4.2.1, 4.2.2	revised PP population criteria

	Section 4.4, 6.3.3	removed descriptions of biomarker and NGF populations and summaries
	Section 5.1.2	specified WOMAC Pain 50% responders as key secondary endpoint to be tested with the Hochberg procedure
	Section 5.2	specified estimands, description of planned on-treatment efficacy assessment period and definition of on- and off-treatment data windows
	Section 5.2.2, 5.2.3, 5.3	specified MMRM analysis using multiply imputed data, and addition of MMRM analysis using all available data, on- or off-treatment; removed analysis of Week 24 data; added analysis of diary pain data for individual Days 1 through 7; specified WPAI analysis using ANCOVA model instead of CMH test
	Section 5.2.4	removed time to event summaries for joint safety events
	Section 6.6	removed AE patient-year summaries, AE plots, summaries of specific AE start day and duration; added NSAID use summaries
	Section 6.6.1	removed Tier 1 and 2 AE graphs
	Section 6.6.2	removed summary of mean change in postural blood pressure
	Section 6.6.3	clarified neurologic data summaries
	Section 6.6.5	clarified joint safety event summaries
	Appendix 2.1	clarified windows for various data types

2. INTRODUCTION

Note: in this document any text taken directly from the protocol is *italicized*.

This SAP provides the detailed methodology for summary and statistical analyses of the data collected in study A4091056. This document may modify the plans outlined in the protocol; however, any major modifications of the primary endpoint definition or its analysis will also be reflected in a protocol amendment.

2.1. Study Objectives

2.1.1. Primary Objective

Demonstrate superior efficacy of tanezumab 2.5 mg administered subcutaneously (SC) and tanezumab 2.5 mg SC titration to 5 mg SC versus placebo at Week 16.

2.1.2. Secondary Objectives

[figure not shown]
Evaluate treatment benefit (efficacy) of a tanezumab 2.5 mg SC titration to 5 mg SC dosing regimen relative to tanezumab 2.5 mg SC alone (descriptive analyses);

Evaluate the safety of tanezumab 2.5 mg SC and tanezumab 2.5 mg SC titration to 5 mg SC regimens.

2.2. Study Design

The study design is summarized in the diagram below.

Figure 1. Study Design

This is a randomized, double-blind, placebo-controlled, multicenter, parallel-group, Phase 3 study of the efficacy and safety of tanezumab when administered by SC injection for 16 weeks compared to placebo in subjects with osteoarthritis of the knee or hip. Approximately 690 subjects (approximately 230 per treatment group) will be randomized to one of 3 treatment groups in a 1:1:1 ratio. Subjects will receive a total of two SC injections, separated by 8 weeks:

- *tanezumab 2.5 mg (Day 1) and tanezumab 2.5 mg (Week 8);*
- *tanezumab 2.5 mg (Day 1), and tanezumab 5 mg (Week 8);*
- *placebo to match tanezumab (Day 1) and placebo to match tanezumab (Week 8).*

The randomization will be stratified by the factors of index joint and highest Kellgren-Lawrence grade in the knee and hip joints.

This study is designed with a total (post-randomization) duration of 40 weeks and will consist of three periods: Screening (up to a maximum of 37 days), Double-blind Treatment (16 weeks, 6 in-clinic visits), and Safety Follow-up (24 weeks). The Screening Period (to begin up to 37 days prior to Randomization) includes a Washout Period (lasting a minimum of 2 days for all prohibited pain medications) if required, and an Initial Pain Assessment Period (IPAP; 7 days prior to Randomization/Baseline; minimum 3 days).

The end of treatment period is at Week 16, with the safety follow-up period up to Week 40. The primary time point for efficacy is Week 16. The period of interest for most safety results is the treatment period. Selected safety results will also be provided separately for the safety follow-up period, and some results will be provided for the combined overall study period comprising the treatment and safety follow-up periods.

3. ENDPOINTS AND BASELINE VARIABLES: DEFINITIONS AND CONVENTIONS

3.1. Primary Endpoint(s)

- *Change from Baseline to Week 16 in the WOMAC Pain subscale;*
- *Change from Baseline to Week 16 in the WOMAC Physical Function subscale;*
- *Change from Baseline to Week 16 in the Patient's Global Assessment of Osteoarthritis.*

Baseline values will be those from the Baseline window as described in Appendix 2.1.

3.2. Secondary Endpoint(s)

3.2.1. Efficacy Measures

- *WOMAC Pain subscale change from Baseline to Weeks 2, 4, 8, 12 and 24;*
- *WOMAC Physical Function subscale change from Baseline to Weeks 2, 4, 8, 12 and 24;*
- *Patient's Global Assessment of Osteoarthritis (5-point Likert scale) change from Baseline to Weeks 2, 4, 8, 12 and 24;*
- *OMERACT-OARSI responder index at Weeks 2, 4, 8, 12, and 16;*

The OMERACT-OARSI responder index at Week X utilizes the change from Baseline to Week X in the WOMAC Pain subscale, the WOMAC Physical Function Subscale and the PGA of Osteoarthritis (using appropriate imputation where necessary for any components). According to this definition, a patient is classified as a responder if, either:

- The improvement from Baseline to Week X was $\geq 50\%$ and ≥ 2 points in either the WOMAC Pain or Physical Function subscales, OR
- At least 2 of the following 3 were true:
 - The improvement from Baseline to Week X was $\geq 20\%$ and ≥ 1 point in the WOMAC Pain subscale;
 - The improvement from Baseline to Week X was $\geq 20\%$ and ≥ 1 point in the WOMAC Physical Function subscale;
 - The improvement from Baseline to Week X $\geq 20\%$ and ≥ 1 point in the PGA of Osteoarthritis (note: from the 5-point Likert scale, any change of ≥ 1 corresponded to a change of $\geq 20\%$).
- *Treatment Response: Reduction in the WOMAC Pain subscale of $\geq 30\%$, $\geq 50\%$, $\geq 70\%$ and $\geq 90\%$ at Weeks 2, 4, 8, 12, and 16;*
- *Cumulative distribution of percent change from Baseline in the WOMAC Pain subscale score to Week 16 (endpoint for summary only);*
- *Treatment Response: Reduction in the WOMAC Physical Function subscale of $\geq 30\%$, $\geq 50\%$, $\geq 70\%$ and $\geq 90\%$ at Weeks 2, 4, 8, 12, and 16;*
- *Cumulative distribution of percent change from Baseline in the WOMAC Physical Function subscale score to Week 16 (endpoint for summary only);*
- *Treatment Response: Improvement of ≥ 2 points in Patient's Global Assessment of Osteoarthritis at Weeks 2, 4, 8, 12, and 16;*

- *Average pain score in the index joint change from Baseline to Weeks 1, 2, 3, 4, 6, 8, 10, 12, 16, 20 and 24;*
- *WOMAC Stiffness subscale change from Baseline to Weeks 2, 4, 8, 12, 16 and 24;*
- *WOMAC Average score change from Baseline to Weeks 2, 4, 8, 12, 16 and 24;*
- *WOMAC Pain Subscale Item: Pain When Walking on a Flat Surface, change from Baseline to Weeks 2, 4, 8, 12, 16 and 24;*
- *WOMAC Pain Subscale Item: Pain When Going Up or Down Stairs, change from Baseline to Weeks 2, 4, 8, 12, 16 and 24;*
- *Work Productivity and Activity Impairment Questionnaire for Osteoarthritis (WPAI:OA) impairment scores change from Baseline to Week 16.*

The WPAI:OA impairment scores are listed below:

- Percent work time missed due to Osteoarthritis.
- Percent impairment while working due to Osteoarthritis.
- Percent overall work impairment due to Osteoarthritis.
- Percent activity impairment due to Osteoarthritis.

The calculation of these endpoints is described in Appendix 3.

- EuroQol 5 Dimension (EQ-5D-5LTM) dimensions and overall health utility score at Baseline, Week 8 and Week 16;

The Baseline and Weeks 8 and 16 responses in the five dimensions (mobility; self-care; usual activities; pain/discomfort; anxiety/depression) and overall health utility score from the EuroQol 5 Dimensions (EQ-5D-5L), and the EQ-VAS will be summarized by treatment group. This summary will use observed data only (no imputation for missing data). The overall health utility score is calculated using the EuroQol value sets, and is described in Appendix 3.

An additional question, called the EQ-VAS asks the patient to rate their health today using a VAS scale from 0 (the worst health you can imagine) to 100 (the best health you can imagine). This will be summarized along with the health utility score.

- *Health Care Resource Utilization at Baseline, Week 24 and Week 40;*
- *Incidence and time to discontinuation due to Lack of Efficacy;*

- *Usage of rescue medication (incidence, number of days) during Weeks 2, 4, 8, 12, 16 and 24;*
- *Usage of rescue medication (amount taken) during Weeks 2, 4, 8, 12, and 16.*

3.3. Other Endpoints

3.3.1. Pharmacokinetic and Pharmacodynamic Measures

- *Plasma tanezumab concentrations;*
- *Serum NGF assessments;*
- *Serum and urine osteoarthritis biomarker concentrations.*

3.4. Baseline Variables

Baseline is generally defined as the last observation prior to first receipt of study drug, within the baseline window as defined in Appendix 2.1.

For analysis of diary pain intensity scores for the index joint, baseline is defined as the mean average daily Pain NRS score using the last 3 values during the final 7 days of the Initial Pain Assessment Period prior to Randomization/Day 1.

The stratification variables are *index joint (hip or knee) and most severe Kellgren-Lawrence grade (of any knee or hip joint)* at study entry (grade 2, 3 or 4).

3.4.1. Covariates

For all models analyzing the continuous primary and secondary efficacy endpoints (except rescue medication) the corresponding Baseline value will be used as a covariate, in addition to Baseline diary average pain. Study site will be fitted as a random effect in the ANCOVA models. The randomization stratification variables of index joint (hip or knee) and highest Kellgren-Lawrence grade (2, 3 or 4) will be included as fixed effects.

A listing of subjects with mis-matches between the stratification variables entered at randomization and the case report form data (including central lab data for Kellgren-Lawrence grade) will be provided. In analysis models, the strata entered at randomization will be used, but for descriptive summarization of the population and identification of subgroups, the strata as indicated on the case report form data will be used.

For the models analyzing the amount and number of days of rescue medication use the model will include terms for Baseline WOMAC Pain, Baseline diary average pain and stratification factors.

The analysis of the incidence of treatment discontinuation due to lack of efficacy will include ... model terms for Baseline WOMAC Pain subscale score, Baseline diary average pain score, index joint, Kellgren-Lawrence grade, and treatment group.

For categorical/binary response endpoints relating to WOMAC Pain and PGA, the corresponding Baseline WOMAC Pain or PGA value will be used as a covariate in the analysis model, in addition to the stratification parameters of index joint and highest Kellgren-Lawrence grade, as well as Baseline diary average pain. For the OMERACT response endpoint, the Baseline WOMAC Pain subscale score and Baseline diary average pain score will be used as covariates in the analysis model, in addition to the stratification parameters of index joint and highest Kellgren-Lawrence grade.

Additional analyses of the three co-primary endpoints will examine the treatment interactions with Study site and Country.

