The incidence ... of use of rescue medication... will be analyzed for Weeks 2, 4, 8, 12, and 16... The incidence of use of rescue medication will be analyzed using logistic regression for binary data, with model terms for Baseline WOMAC Pain subscale score, Baseline diary average pain, index joint, Kellgren-Lawrence grade, and treatment group. ... Estimated levels of rescue medication use will be shown for each treatment group, and the ratio (with

95% CI) for comparisons versus placebo will be shown. Imputation for missing rescue medication data will use LOCF only.

The incidence of treatment withdrawal due to lack of efficacy ('Insufficient Clinical Response' on the Subject Summary Case Report form) will also be analyzed for discontinuation up to Week 16 (end of treatment period). The analysis of the incidence of discontinuation due to lack of efficacy will be made using logistic regression for binary data, with model terms for Baseline WOMAC Pain subscale score, Baseline diary average pain score, index joint, Kellgren-Lawrence grade, and treatment group. Discontinuation in the post-treatment safety follow-up period will not be included in this endpoint for analysis, but will be summarized as part of the safety tables.

Cumulative WOMAC Pain response and WOMAC Physical Function at Week 16 using response definitions from a reduction of >0% to =100% (in steps of 10%) will be summarized, using mixed BOCF/LOCF (as described above), and also LOCF and BOCF imputation for WOMAC Pain and WOMAC physical function. Imputation with BOCF for subjects with missing data at that timepoint will lead to the subjects being assessed as non-responders for the response endpoint.

The proportion of subjects who meet a WOMAC Pain response definition at Week 16 will be examined in the cohort of subjects who had a WOMAC Pain response to treatment at Week 8 and the cohort of subjects who did not have a WOMAC Pain response at Week 8. Treatment comparisons will be made within each cohort for tanezumab 2.5/5 mg versus placebo and tanezumab 2.5 mg versus placebo. A descriptive comparison will also be made between the treatment groups of tanezumab 2.5/5 mg versus tanezumab 2.5 mg. These analyses will be produced for the WOMAC Pain response levels of 30% and 50%, and other response definitions (15%). This is an exploratory analysis as treatment comparisons are not specifically powered to achieve significance within cohorts of subjects.

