The rescue medication data will be converted to Weekly scores for the week prior to the timepoint of interest. Calculation of the endpoints is described in Appendix 3.

The ... number of days of use of rescue medication ... will be analyzed for Weeks 2, 4, 8, 12, and 16... and the amount of rescue medication use per week will be analyzed for Weeks 2, 4, 8, 12, and 16. ... The number of days and amount of rescue medication (mg dosage of acetaminophen) will be analyzed using the Negative Binomial model, with model terms of Baseline WOMAC Pain subscale score, Baseline diary average pain score, index joint, Kellgren-Lawrence grade, and treatment group. In this model the error term is defined with a negative binomial distribution, and 'log' is used as the link function. Estimated levels of rescue medication use will be shown for each treatment group, and the ratio (with 95% CI) for comparisons versus placebo will be shown. Imputation for missing rescue medication data will use LOCF only. For this analysis, Baseline data will not be carried forward in the case of a post-Baseline observation not being available for use in LOCF.

A table showing number and percentage of subjects will summarize the response for each dimension (item) for the EQ-5D-5L™ at Baseline and Week 8 and Week 16. These summary tables will be shown by treatment group. In addition, for each treatment and for each time point assessed, descriptive statistics (mean, standard deviations, median, number of subjects) will characterize the five-item health status profile on the EQ-5D-5L™ in terms of the health utility score, and the EQ-Visual Analog Scale (EQ-VAS).

The HCRU data at Baseline, Week 24, and Week 40 will be summarized.

Summaries of the change from Baseline to Week 16 in the WPAI:OA impairment scores will be shown by treatment group. This summary will use observed data only (no imputation for missing data). The calculation of these endpoints is described in Appendix 3.

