For the analysis of the rescue medication endpoints, missing data is imputed for daily missing scores first, and then the last available weekly score (after daily missing data is imputed) will be used for subsequent missing weekly scores, as described below. While subjects are still in the study any missing data will be imputed by carrying forward the last recorded daily data up to Week 16 (LOCF daily data). Imputation using the daily data will occur up to the end of the last week when the subject is in the study (see Appendix 2.1 for definitions of the last study day in each week). For example if a subject discontinues on study day 10, then data up to the end of Week 2 will be imputed in this way. The weekly scores for the rescue medication endpoints can then be calculated for each week the subject is in the study. Rescue medication endpoints are summarized and analyzed using LOCF, and so the last weekly score for the rescue medication will be used for LOCF after the subject has discontinued from the study (note, imputation is taken from the last week with non-missing data and not necessarily from the last available study week, e.g. if Week 8 is missing then Week 7 data can be used). The baseline observation will not be carried forward in the case where a post-baseline observation is not available for the LOCF imputation. In the example above, the subject who discontinued in Week 2 (Study Day 10) will have their Week 2 value used as the LOCF value for all Weeks 3-16. The BOCF imputation rule will not be used for the subject because rescue medication is collected during the Initial Pain Assessment Period only (days -7 to -1) and subjects should not be taking rescue medication within 24 hours of the Baseline visit (so part of day -1), therefore Baseline rescue medication use is not an accurate reflection of subjects' true Baseline use of rescue medication. Imputation of weekly diary data after Week 16 will not be performed.

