Number of days of rescue medication use during Weeks 2, 4, 8, 12, and 16	ITT	Negative Binomial Model	BL WOMAC Pain, BL diary average pain, Index Joint (Knee/Hip), Highest KL grade (2, 3 or 4), Treatment Group	LOCF	Secondary Endpoint Analysis
Amount (mg) of rescue medication taken during Weeks 2, 4, 8, 12, and 16	ITT	Negative Binomial Model	BL WOMAC Pain, BL diary average pain, Index Joint (Knee/Hip), Highest KL grade (2, 3 or 4), Treatment Group	LOCF	Secondary Endpoint Analysis
EQ-5D-5L dimensions (Mobility; Self-care; Usual activities; Pain/Discomfort; Anxiety/Depression), EQ-VAS and Overall Health Utility at Baseline and Weeks 8 and 16	ITT	Summary	NA	Observed	Secondary Endpoint Analysis
WPAI endpoints (% work time missed; % impairment while working; % overall work impairment; % activity impairment) at Week 16	ITT	ANCOVA	BL score, BL diary average pain, Index Joint (Knee/Hip), Highest KL grade (2, 3 or 4), Treatment Group (study site as a random effect)	Observed	Secondary Endpoint Analysis
Healthcare Resource Utilization at Baseline, Weeks 24 and 40	ITT	Descriptive Summary	Treatment group	Observed	Secondary Endpoint Analysis
Change from baseline to Weeks 2, 4, 8, 12, 16, 24, and 40 in the NIS score, and Change from Baseline to Worst post-Baseline NIS score	ITT	CMH test	Treatment Group [1]	LOCF (Weeks 2, 4, 8, 12, 16, 24, & 40), Worst post-baseline score	Safety Endpoint Analysis
Survey of Autonomic Symptoms (SAS), number of symptoms and total impact score (by visit and change from Baseline)	ITT	Summary	NA	Observed	Safety Endpoint Analysis

[1] CMH test will be stratified by the levels of the combined stratification parameters (6 levels). If there are <15 subjects in any combined stratification level then the CMH test will be unstratified

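### Days and amount of rescue medication are the only continuous efficacy endpoints modelled without their own Baseline value, although rescue use is recorded before randomisation

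*SAP*

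**What the plan says.** Section 3.4.1 gives the rule and its exception: "For all models analyzing the continuous primary and secondary efficacy endpoints (except rescue medication) the corresponding Baseline value will be used as a covariate". For days and amount of rescue use, the same section says that "the model will include terms for Baseline WOMAC Pain, Baseline diary average pain and stratification factors". Section 5.2.2 repeats this: the two endpoints "will be analyzed using the Negative Binomial model, with model terms of Baseline WOMAC Pain subscale score, Baseline diary average pain score, index joint". The rest of that list is KL grade and treatment, and the link is log. The Appendix 1 rows for number of days and for "Amount (mg) of rescue medication taken during Weeks 2, 4, 8, 12, and 16" list the same terms.

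Section 5.3 shows that a pre-randomisation measure exists: "rescue medication is collected during the Initial Pain Assessment Period only (days -7 to -1"). It adds that no rescue should be taken in the 24 hours before the Baseline visit, which affects part of day -1. It concludes that Baseline rescue use does not accurately reflect true Baseline use, and gives this as the reason for not using BOCF. Section 2.2 sets the Initial Pain Assessment Period (IPAP) at 7 days with a minimum of 3.

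Incidence of rescue use is a separate, binary endpoint. Section 5.2.1 states: "The incidence of use of rescue medication will be analyzed using logistic regression for binary data, with model terms for Baseline WOMAC Pain subscale score". The other terms in that model are diary pain at Baseline, the stratification factors and treatment.

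**The concern.** In a randomised comparison, a covariate need only be measured before randomisation and predict the outcome. Pre-randomisation rescue use meets the first condition and plausibly the second, because a person's habit of taking acetaminophen need not be fully captured by pain scores. Section 3.4.1 gives no reason for the exception. The reservation in section 5.3 answers a different question. A value imputed as an outcome has to stand in for the missing outcome, so its accuracy matters directly. Error in a covariate shrinks the gain in precision but does not bias the treatment comparison.

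At stake is the width of the confidence intervals for the ratio versus placebo for days and amount, and the chance of detecting a real difference on these two secondary endpoints.

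**Working it through.** **1. Is the exception unique among continuous endpoints?** Sections 3.4.1 and 5.2.2 and Appendix 1 give an own-Baseline term to the WOMAC subscales, the WOMAC Average and the two pain items, the PGA, diary pain and the four WPAI scores. Days and amount of rescue medication have none. EQ-5D-5L and health care resource use are only summarised. So the two rescue endpoints are the only modelled continuous efficacy endpoints without an own-Baseline term.

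**2. Is the value usable?** The restriction touches part of day -1, so days -7 to -2 lie outside it. The SAP already takes a covariate from the same window: Baseline diary pain is the mean of the last 3 scores in the 7 days before Day 1, or of fewer if fewer exist (sections 3.4 and 5.3, Appendix 2.1).

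**3. Size of the gain.** The SAP states no power, dispersion or correlation for the rescue endpoints, so there is no planned figure to reproduce.

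Inputs: two-sided 5% level (sections 5.1.1 and 5.1.2); about 230 subjects per group (section 2.2); base power 80% (assumed); r, the partial correlation of the new covariate with the outcome given the terms already in the model (assumed).

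Linear approximation: SE ratio = √(1 − r²); power = Φ((1.960 + 0.842)/√(1 − r²) − 1.960); equivalent subjects per group = 230/(1 − r²).

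| r | SE ratio | Power from 80% | Equivalent n per group |
|---|---|---|---|
| 0 | 1.000 | 80.0% | 230 |
| 0.2 | 0.980 | 81.6% | 240 |
| 0.3 | 0.954 | 83.6% | 253 |
| 0.5 | 0.866 | 89.9% | 307 |

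For example, at r=0.3: 2.802/0.954 = 2.937; 2.937 − 1.960 = 0.977; Φ(0.977) = 83.6%.

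**4. Check under a negative binomial model.** Simulation with 230 per arm, two arms and 150 runs per setting; a mean of about 6 weekly doses, a log ratio of −0.3 and a pain covariate, all assumed. Mean SE of the log ratio without and with log(1 + pre-randomisation doses):

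| Between-subject SD of log rescue propensity | Without | With | Ratio |
|---|---|---|---|
| 0 | 0.0612 | 0.0612 | 1.00 |
| 0.25 | 0.0652 | 0.0648 | 0.99 |
| 0.5 | 0.0757 | 0.0710 | 0.94 |
| 0.8 | 0.0938 | 0.0770 | 0.82 |

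The range is similar: no gain to about 18% off the SE. Where the covariate carried no information, it cost nothing visible.

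**5. Effect of a short IPAP.** With a 3-day IPAP, days -7 to -2 hold only two entries (days -3 and -2). Under an assumed logit-normal daily-use model with a week-to-week SD of 1.2, values of r near 0.20, 0.36 and 0.53 with six days fall to about 0.16, 0.29 and 0.46 with two. By the formula above, power changes from 81.6%, 85.1% and 91.0% to 81.0%, 83.3% and 88.4%. This is the worst case, with every IPAP at its minimum.

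**6. Incidence.** In a separate simulation (400 runs per setting, assumed inputs), adding the covariate to the logistic model gave no gain at r=0.2, 46% to 49% at r=0.36, and 40% to 47% at r=0.53. Base power differs between settings, so the gains are not comparable across r.

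**The case against.** The strongest reply is that the choice is deliberate, disclosed and applied consistently. The SAP says openly that it distrusts Baseline rescue use, two Baseline pain covariates are already in the models, and the comparison is valid under randomisation without the extra term. All of that stands. It makes this a matter of efficiency, not of error. It does not supply a reason for the omission, since the stated distrust concerns BOCF.

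The second reply is that the size rests wholly on an assumed r. That also stands. The documents do not show that pre-randomisation rescue use is the strongest predictor available, and a short IPAP weakens it.

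Three stronger readings are tempting, and the SAP does not support them.

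- A reader might infer that the rescue models are the only efficacy models without an own Baseline. They are not. The CMH test of the PGA uses the strata only, the OMERACT-OARSI model carries the Baseline of one of its three components, and the analyses of discontinuation for lack of efficacy have no own Baseline to use.
- A reader might treat rescue use as the SAP's direct check on whether analgesics confound the pain results. Section 5.2 says only that efficacy data are kept regardless of rescue use, and section 3.2.1 lists the rescue endpoints among many secondary ones.
- A reader might extend the change to incidence. The simulated gain there is absent or small at low to moderate r. In logistic regression, a further prognostic covariate also changes the conditional odds ratio being estimated.

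**Conclusion.** The point holds for days and amount of rescue medication. The planned comparisons are unbiased, but they leave aside a pre-randomisation measure of the same endpoint for a reason that does not apply to a covariate. From an assumed 80% power, the gain would be about 2 points at r=0.2, 4 at r=0.3 and 10 at r=0.5, less with short IPAPs, and nil if r is zero. These figures assume the base power, r and a linear-model approximation, none of which comes from the SAP.

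The endpoints are secondary and outside the type I error control of section 5.1.2, so no confirmatory conclusion depends on this. It is worth doing because it is nearly free, not because the plan is unsound without it.

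**What to change.** - In section 3.4.1, remove the exception for rescue medication. There, in section 5.2.2 and in the two Appendix 1 rows for days and amount, add pre-randomisation rescue use as a covariate in the negative binomial models.
- Derive it from the available diary days -7 to -2, scaled to the number of recorded days: days used for the days model, and tablets for the amount model (or days used, if tablet counts are not recorded in that period). State the scale on which it enters; log(1 + x) is the form used in the check above.
- If a subject has no entry on those days, use the all-arm mean so that nobody is dropped. Section 5.3 already fills in a missing Baseline diary pain covariate for the same purpose.
- Keep the rule that Baseline rescue use is not carried forward as an outcome, and leave the incidence model as it is.

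The cost is one derived covariate from data already collected, a few wording changes before unblinding, and slight non-comparability with earlier studies analysed without it.
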